7.4.1. Study recording period and follow-up for AEs and SAEs

AEs and SAES will be recorded from time of first protocol-specific intervention throughout the treatment period and including the follow-up period (90 days after the last dose of Durvalumab and/or MEDI0457). For physical exams, only abnormal findings will be recorded.

During the course of the study all AEs and SAEs should be proactively followed up for each subject. Every effort should be made to obtain a resolution for all events, even if the events continue after discontinuation/study completion.

If a subject discontinues from treatment for reasons other than disease progression, and therefore continues to have tumor assessments, drug or procedure-related SAEs must be captured until the patient is considered to have confirmed PD and will have no further tumor assessments.

The investigator is responsible for following all SAEs until resolution, until the subject returns to baseline status, or until the condition has stabilized with the expectation that it will remain chronic, even if this extends beyond study participation.

7.4.2. Follow-up of unresolved adverse events

Any AEs that are unresolved at the subject's last visit in the study are followed up by the investigator for as long as medically indicated, but without further recording in the case report form. After 90 days, only subjects with ongoing IP-related SAEs will continue to be followed for safety.

AstraZeneca retains the right to request additional information for any subject with ongoing AE(s)/SAE(s) at the end of the study, if judged necessary.

Version Number: 1.8 Date: July 26, 2019

Proprietary of MD Anderson Cancer Center

7.4.3. Reporting to FDA

Serious adverse events will be forwarded to FDA by the MDACC IND Office (Safety Project Manager IND Office) according to 21 CFR 312.32.

It is the responsibility of the PI and the research team to ensure serious adverse events are reported according to the Code of Federal Regulations, Good Clinical Practices, the protocol guidelines, the sponsor's and supporting companies' guidelines, and Institutional Review Board policy.

7.4.4. Investigator Communications with AstraZeneca

A copy of the SAE report must be sent to AstraZeneca at the time the event is reported to the FDA. SAE report forms should be forwarded with supporting relevant source documents (e.g. history and physical [H&P], hospital discharge summary, autopsy report when available, results of relevant diagnostic tests completed to evaluate the event) to AstraZeneca's designated mailbox: [contact].

Transmission of the SAE report Form should be confirmed by the site personnel submitting the report.

Follow-up information for SAEs and information on non-serious AEs that become serious should also be reported to AstraZeneca as soon as it is available; these reports can be submitted using the MD Anderson eSAE Report Form.

7.5. Adverse Events of Special Interest

An AESI is of scientific and medical interest specific to understanding of the IP and may require close monitoring and rapid communication by the investigator to the supporting companies. An AESI may be serious or non-serious. The rapid reporting of AESIs allows ongoing surveillance of these events in order to characterize and understand them in association with the use of this IP.

Adverse events of special interest for MEDI0457 and durvalumab include but are not limited to events with a potential inflammatory or immune-mediated mechanism and which may require more frequent monitoring and/or interventions such as steroids, immunosuppressants and/or hormone replacement therapy. These AESIs are being closely monitored in clinical studies with durvalumab monotherapy and combination therapy. An irAE is defined as an AE that is associated with drug exposure and is consistent with an immune-mediated mechanism of action and where there is no clear alternate etiology. Serologic, immunologic, and histologic (biopsy) data, as appropriate, should be used to support an irAE diagnosis. Appropriate efforts should be made to rule out neoplastic, infectious, metabolic, toxin, or other etiologic causes of the irAE. If the Investigator has any questions in regards to an AE being an irAE, the Investigator should promptly contact the Study Physician. Identified risks (listed/expected reactions) for durvalumab include: diarrhea, ALT increase, AST increase, pneumonitis, and colitis/enterocolitis.

Version Number: 1.8 Date: July 26, 2019 Proprietary of MD Anderson Cancer Center

Adverse events of special interest observed with MEDI0457 and durvalumab include:

- Colitis,
- Pneumonitis,
- ALT/AST increases/hepatitis/hepatotoxicity,
- Neuropathy/neuromuscular toxicity (i.e., events of encephalitis, peripheral motor and sensory neuropathies, Guillain-Barré, and myasthenia gravis),
- Endocrinopathy (i.e., events of hypophysitis, adrenal insufficiency, type 1 diabetes, and hyper- and hypothyroidism),
- Dermatitis,
- Nephritis,
- Pancreatitis (or laboratory tests suggestive of pancreatitis increased serum lipase, increased serum amylase),
- Infusion-related reactions, and
- Administration site reactions.

Adverse events of special interest are required to be reported within 24 hours of knowledge of the event in the database, even if the event is considered to be non-serious.

Further information on these risks (e.g., presenting symptoms) can be found in the subsections below and the current versions of the IBs. More specific guidelines for their evaluation and treatment are described in detail in Appendix D.

7.5.1. **Colitis**

Diarrhea, colitis, and enterocolitis are irAEs that have been reported with durvalumab. In rare cases, colon perforation may occur that requires surgery (colectomy) or can lead to a fatal outcome if not properly managed. Diarrhea/colitis in patients receiving durvalumab should be managed as per the guidelines for the management of diarrhea and enterocolitis in **Appendix D**.

7.5.2. **Pneumonitis**

AEs of pneumonitis are also of interest for the Supporter. Initial work-up should include highresolution CT scan, ruling out infection, and pulse oximetry. Pulmonary consultation is highly recommended. Guidelines for management of patients with pneumonitis are outlined in Appendix D.

7.5.3. Hypersensitivity reactions

Hypersensitivity reactions as well as infusion-related reactions have been reported with anti-PD-L1 and anti-PD-1 therapy (Brahmer et al 2012). As with the administration of any foreign protein and/or other biologic agents, reactions following the infusion of monoclonal antibodies can be caused by various mechanisms, including acute anaphylactic (immunoglobulin Emediated) and anaphylactoid reactions against the monoclonal antibodies, and serum sickness. Acute allergic reactions may occur, may be severe, and may result in death. Acute allergic

Version Number: 1.8 Date: July 26, 2019

Proprietary of MD Anderson Cancer Center

reactions may include hypotension, dyspnea, cyanosis, respiratory failure, urticaria, pruritus, angioedema, hypotonia, urticaria, arthralgia, bronchospasm, wheeze, cough, dizziness, fatigue, headache, hypertension, myalgia, vomiting and unresponsiveness. Guidelines for management of patients with hypersensitivity reactions (including anaphylactic reactions) are outlined in **Appendix D**.

7.5.4. Infusion-related reactions

AEs of infusion reactions (also termed infusion-related reactions) are of special interest to the supporting companies and are defined, for the purpose of this protocol, as all AEs occurring from the start of the study treatment infusion up to 48 hours after the infusion start time. All infusion reactions should be documented in the database, and all infusions-related reaction SAEs should be reported as described in Section 7.4. Guidelines for management of patients with infusion-related reactions are outlined in **Appendix D**.

7.5.5. Administration site reactions

Adverse events of administration site reactions are of special interest to the supporting company. These are defined, for the purpose of this protocol, as all AEs occurring as a result of the administration of the study treatment (vaccine and/or EP) of grade ≥ 3 pair or any other administration site reaction. Guidelines for the grading and management of administration site reactions are outlined in **Appendix E**.

7.6. Other events requiring reporting

7.6.1. Overdose

An overdose is defined as a subject receiving a dose of Durvalumab and/or MEDI0457 in excess of that specified in the IB, unless otherwise specified in this protocol.

Any overdose of a study patient with IP, with or without associated AEs/SAEs, is required to be reported within 24 hours of knowledge of the event to the supporting companies' designee and the MDACC IND Office. If the overdose results in an AE, the AE must also be recorded as an AE.

Overdose does not automatically make an AE serious, but if the consequences of the overdose are serious, for example death or hospitalization, the event is serious and must be recorded and reported as an SAE. There is currently no specific treatment in the event of an overdose of either MEDI0457 or durvalumab.

The investigator will use clinical judgment to treat any overdose.

7.6.2. Maternal exposure

If a patient becomes pregnant during the course of the study, the IPs should be discontinued immediately.

Pregnancy itself is not regarded as an AE unless there is a suspicion that the IP under study may have interfered with the effectiveness of a contraceptive medication. Congenital abnormalities or birth defects and spontaneous miscarriages should be reported and handled as SAEs. Elective

Version Number: 1.8 Date: July 26, 2019

Proprietary of MD Anderson Cancer Center

abortions without complications should not be handled as AEs. The outcome of all pregnancies (spontaneous miscarriage, elective termination, ectopic pregnancy, normal birth, or congenital abnormality) should be followed up and documented even if the patient was discontinued from the study.

If any pregnancy occurs in the course of the study, then the Investigator or other site personnel should inform the appropriate AstraZeneca representatives within 1 day, i.e., immediately, but **no later than 24 hours** of when he or she becomes aware of it.

The designated AstraZeneca representative will work with the Investigator to ensure that all relevant information is provided to the AstraZeneca Patient Safety data entry site within 1 to 5 calendar days for SAEs and within 30 days for all other pregnancies.

The same timelines apply when outcome information is available.

7.6.3. Paternal Exposure

Male patients must refrain from fathering a child or donating sperm during the study since the potential for chromosomal aberrations in male gametes, and possible teratogenic effects thereof, has not yet been thoroughly investigated. Male patients who are sexually active must use a barrier (condom with spermicide) method of contraception from the first dose until 90 days after the last dose of IP.

Pregnancy of the patients' partners is not considered to be an AE. However, the outcome of all pregnancies (spontaneous miscarriage, elective termination, normal birth, or congenital abnormality) should be followed up and documented.

If any pregnancy occurs in the course of the study, then investigators or other site personnel must inform the appropriate AstraZeneca representatives within 1 or 5 days.

7.6.4. Hepatic Function Abnormality

Hepatic function abnormality (i.e., TBL, ALT, or AST outside of the levels defined in the inclusion criteria) in a study patient, with or without associated clinical manifestations, is required to be reported as "hepatic function abnormal" within 24 hours of knowledge of the event to the MDACC IND Office and supporting companies or designee unless a definitive underlying diagnosis for the abnormality (e.g., cholelithiasis or bile duct obstruction) that is unrelated to IP has been confirmed.

If the definitive underlying diagnosis for the abnormality has been established and is unrelated to IP, the decision to continue administration of the study patient will be based on the clinical judgment of the investigator.

If no definitive underlying diagnosis for the abnormality is established, administration of IP to the study patient must be interrupted immediately. Follow-up investigations and inquiries must be initiated by the investigational site without delay. Each reported event of hepatic function abnormality will be followed by the investigator and evaluated by the supporting companies.

Version Number: 1.8 Date: Inly 26, 2019 Proprietary of MD Anderson Cancer Center

7.6.5. Hy's Law

Cases where a patient shows elevations in liver biochemistry may require further evaluation and occurrences of AST or ALT \geq 3 x ULN together with TBL \geq 2 x ULN may need to be reported as SAEs. Please refer to Appendix B for further instruction on cases of increases in liver biochemistry and evaluation of Hy's Law (HL).

7.6.6. **Events requiring reporting within 72 hours**

The following events must be reported to MDACC IND Office and supporting companies within 72 hours of the occurrence of the event to discuss whether further administration should continue for the participant.

- Grade 3 or greater injection site reaction.
- Grade 3 or greater fever, not associated with above listed events (a to f) in Section 6.7.2, assessed by Principal Investigator as related to study treatment.
- Grade 3 or greater systemic symptoms, not associated with above listed events (a to e) in Section 6.7.2, assessed by Principal Investigator as related to study treatment.

STATISTICAL ANALYSES 8.

8.1. **Statistical Considerations**

Summary statistics will be provided to summarize response, toxicity, and other clinical and demographic variables. Objective response rate and disease control rate by RECIST 1.1 criteria will be estimated with 95% confidence interval. Progression free survival and OS will be summarized using the method of Kaplan and Meier and Cox proportional hazards models. All analysis will be done across all cohorts along with subset analysis within each cohort.

8.1.1. Sample size estimate

Up to 77 evaluable patients will be enrolled in this study.

The design requires a maximum of 34 evaluable subjects per cohort. Nine subjects will be treated in the first stage. If 1 or fewer responses are seen, enrollment into that cohort will be stopped for futility. If there are 2 or more responses, an additional 25 subjects will be enrolled into the second stage. If there are 9 or more responses out of 34, the combination will be deemed worthy of further study. The two cohorts with the best response rates after completion of accrual into stage 1 for all 3 cohorts will move on to stage 2. The maximum total sample size is 77 (9 x 1 cohorts + 34 x 2 cohorts) evaluable subjects.

After each cohort completes accrual to stage I, only the two cohorts with the most responses will move on to stage 2. Therefore, accrual to stage 2 will not start till all three cohorts have completed stage I. However, if a single cohort has a high response rate (≥4 responses out of 9 patients), the second stage of accrual may proceed prior to other cohorts completing stage I.

Version Number: 1.8 Date: July 26, 2019 Proprietary of MD Anderson Cancer Center

8.1.2. **Efficacy futility assessments**

We will use a Simon's two-stage optimal design targeting an alternative hypothesis ORR of 0.35 versus a null hypothesis ORR of 0.15 with 80% power and a one-sided 0.05 significance level. This will be conducted independently in each of the three cohorts. ORR will be assessed every 8 weeks and will be defined using RECIST 1.1 criteria. During the interim, the accrual will be halted until the go/no-go decision can be made.

8.1.3. **Toxicity monitoring**

DLT will be monitored continuously in cohorts of 6 subjects for all 34 subjects to ensure safety using the methods by Thall et al. Cohorts will be monitored independently. The trial will be stopped early for toxicity if the $Pr(DLT > 30\% \mid data) > 0.90$ using a prior of beta (0.6, 1.4) for toxicity. Stopping boundaries corresponding to this probability criterion are to halt the trial if (# of patients with DLT) / (# patients evaluated) $\geq 4/6$, 6/12, 9/18, 11/24, and 13/30. The operating characteristics of this rule is found in table below.

Table 5. Operating Characteristics of Stopping Rules for Toxicity

True toxicity	P(stop)	p10	p25	p50	p75	p90	Avg # subjects	Avg # toxicities
0.10	0.002	34	34	34	34	34	33.9	3.4
0.20	0.035	34	34	34	34	34	33.2	6.7
0.30	0.196	12	34	34	34	34	29.9	9.0
0.40	0.549	6	12	30	34	34	23.2	9.2
0.50	0.877	6	6	12	24	34	15.5	7.8

The Investigator is responsible for completing toxicity/efficacy summary reports and submitting them to the IND office Medical Affairs and Safety Group for review. These should be submitted as follows:

Toxicity Assessment: After the first 6 evaluable patients per cohort, complete 4 weeks of study treatment, and every 6 evaluable patients thereafter.

Efficacy Assessment: After the first 9 evaluable patients per cohort, complete 8 weeks of study treatment, and every 5 evaluable patients thereafter, until enrollment is complete. On every report submission, the response information from previous reported patients will need to be updated.

A copy of the cohort summary should be placed in the Investigator's Regulatory Binder under "sponsor correspondence".

Version Number: 1.8 Date: July 26, 2019

Proprietary of MD Anderson Cancer Center

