1.6. Study Design

This study will be an open label, multi-cohort, phase II trial for the combination therapy of MEDI0457 (INO-3112) and Durvalumab (MEDI4736) in patients with HPV-16 and/or -18 related malignancies. This study will enroll 3 cohorts of patients with HPV-16/18 (+) tumors. The three cohorts are:

- 1. HPV-16/18 cervical cancer,
- 2. HPV-16/18 rare tumors (anal, penile, vulvar, vaginal), and
- 3. HIV (+) HPV-16/18 malignancies (any site).

Each cohort will have a two-stage design with predetermined stopping rules based on ORR after stage I and each cohort will function independently clinically. After each cohort completes accrual to stage I, only the two cohorts with the most responses will move on to stage 2.

Therefore, accrual to stage 2 will not start till all three cohorts have completed stage I. However, if a single cohort has a high response rate (≥4 responses out of 9 patients), the second stage of accrual may proceed prior to other cohorts completing stage I.

At the onset of the study, only patients with cervical, vulvar, or vaginal cancers will be enrolled for the first 3 slots. Once all 3 of these patients have completed the first 6 weeks of treatment, enrollment will be opened to all included cancer histotypes.

Both MEDI0457 and durvalumab treatment will continue until confirmed disease progression or unacceptable toxicity. Either treatment may be stopped by the investigator if a SAE is deemed to be related to that treatment while the other treatment continues.

The target population consists of male or female patients 18 years of age or older with recurrent or metastatic HPV 16- or 18-associated cancers with persistent or progressive disease (PD) after initial standard-of-care treatment and lacking a curative treatment option.

Eligible patients must have at least one "measurable target lesion"—according to RECIST version 1.1—that has not been previously irradiated. In addition, if the primary lesion is not large enough for a biopsy without changing radiologic findings for following response, one additional lesion

Version Number: 1.8 Date: July 26, 2019

Proprietary of MD Anderson Cancer Center

that can be safely biopsied at screening and prior to the first dose of MEDI0457 at Week 1 will be required.

All patients will receive combination treatment with MEDI0457 and durvalumab as per the **Planned Dosing Schedule (Section 4.4.1, Figure 1**, and **Table 3**).

[figure not shown]

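### The stated 80% power per cohort ignores the two-cohort limit on stage 2; with the limit it is about 61% to 79% in the scenarios examined

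*Combined protocol and SAP*

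**What the plan says.** Section 8.1.2 specifies the efficacy design: "We will use a Simon's two-stage optimal design targeting an alternative hypothesis ORR of 0.35". The target is set there "versus a null hypothesis ORR of 0.15 with 80% power and a one-sided 0.05 significance level". It adds: "This will be conducted independently in each of the three cohorts".

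Section 8.1.1 gives the boundaries. "Nine subjects will be treated in the first stage"; one response or none closes the cohort for futility. "If there are 2 or more responses, an additional 25 subjects will be enrolled into the second stage", and 9 or more responses among 34 count as success.

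The same section then limits entry to stage 2: "The two cohorts with the best response rates after completion of accrual into stage 1 for all 3 cohorts will move on", and again "only the two cohorts with the most responses will move on to stage 2". The maximum of 77 evaluable patients is built on that limit (9 × 1 + 34 × 2 = 77). A cohort with at least 4 responses among 9 may begin stage 2 before the others finish stage 1. Section 1.6 repeats both rules, next to the statement that "each cohort will function independently clinically".

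No section gives power under the limit or says which cohort advances when the last stage 2 place is tied.

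**The concern.** The two statements in 8.1.1 about who enters stage 2 differ. One depends only on the cohort's own count (2 or more among 9). The other depends on how that count ranks against the other two cohorts. The 80% in 8.1.2 follows from the first rule alone, yet the trial will apply both.

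The stake is how a cohort that does not advance is read. If the combination works in all three cohorts, one of them will often be closed despite passing its futility rule. A reader who relies on 80% power could take that cohort as a negative result, although ranking, not lack of response, closed it. With nine patients per cohort, ties for the last place will also be common, and the plan leaves them to an ad hoc decision.

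**Working it through.** **Inputs.** From 8.1.1 and 8.1.2: null rate 0.15, target rate 0.35, 9 patients in stage 1, stop at ≤1, 25 more patients in stage 2, success at ≥9 of 34, at most two of three cohorts in stage 2. Assumed, because the documents are silent: the true response rates of the other two cohorts (0.15, 0.25 or 0.35) and the tie rule. The ≥4/9 clause is read as affecting timing only.

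**Step 1: the plan's own figure.** Write b(x; n, p) for the binomial probability. For one cohort alone,

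power = Σ(x = 2 to 9) b(x; 9, 0.35) × P(Bin(25, 0.35) ≥ 9 − x).

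The chance of stopping at stage 1 is 0.65⁹ + 9 × 0.35 × 0.65⁸ = 0.0207 + 0.1004 = 0.121, so entry to stage 2 is 0.879. The sum gives power 0.811. The same formula at 0.15 gives type I error 0.047, with early stopping 0.5995 and expected sample size 19.01. A search over two-stage designs confirms that 1/9 and 8/34 are the Simon optimal boundaries. The stated 80% and 0.05 are therefore correct for a single cohort.

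**Step 2: add the limit.** Let x be the count in the cohort of interest and y, w the counts in the other two, with rates q₁, q₂. Let c be the number of other cohorts with more than x responses and t the number with exactly x. With random tie-breaking, the chance of advancing given x ≥ 2 is

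A = min(1, (2 − c)/(t + 1)) if c ≤ 1, and A = 0 if c = 2.

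Then

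power = Σₓ₌₂..₉ Σᵧ Σ_w b(x; 9, 0.35) b(y; 9, q₁) b(w; 9, q₂) × A × P(Bin(25, 0.35) ≥ 9 − x).

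Summing over all stage 1 outcomes:

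| Other two cohorts' rates | Power, random ties | Always loses ties | Always wins ties |
|---|---|---|---|
| no limit applied | 0.811 | – | – |
| 0.15 and 0.15 | 0.794 | 0.777 | 0.807 |
| 0.25 and 0.25 | 0.732 | 0.677 | 0.775 |
| 0.35 and 0.15 | 0.759 | 0.722 | 0.791 |
| 0.35 and 0.35 | 0.614 | 0.527 | 0.688 |

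A simulation of 2,000,000 trials gave 0.795, 0.732, 0.759 and 0.613 for the four limited scenarios in table order.

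**Step 3: where the loss sits, all three at 0.35.**

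- Entry to stage 2 falls from 0.879 to 0.653. The difference, 0.8789 − 0.6526 = 0.2263, is the chance of passing stage 1 and not being advanced.
- The power lost is 0.811 − 0.614 = 0.197. This is the chance that the cohort passes, is not advanced, and would have reached 9 of 34. As a share of those not advanced, 0.197 / 0.2263 = 87%.
- All three cohorts pass stage 1 with probability 0.879³ = 0.679. The last place is tied in 24.9% of trials.
- Power given entry is 0.6138 / 0.6526 = 0.941 with the limit and 0.8107 / 0.8789 = 0.922 without. A cohort that enrols 34 and misses 9 is therefore not weaker evidence.
- At least one cohort succeeds with probability 0.992.

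**Step 4: type I error.** For a cohort at 0.15 it is 0.046 with both others at 0.15 and 0.031 with both others at 0.35, against 0.047 without the limit.

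**The case against.** The limit is not hidden: 8.1.1 states it twice and builds the 77 on it, and 1.6 repeats it. Independence in 8.1.2 can be read as each cohort having its own boundaries, and 80% is a true property of the Simon design named there. The phrase in 1.6 about cohorts functioning independently concerns clinical conduct and is little support for a claim about power. All of that is fair. It makes this a gap between a stated property and the full rule, not a slip in the single-cohort sum.

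The size of the loss also depends on rates the plan does not give. With both other cohorts at the null, power is 79.4%, only 0.6 points below the stated 80%. The 61% needs all three at 0.35, where the trial as a whole is almost certain to find something. Nor is 61% a floor: with both others at 0.50 it is about 38%. This stands, and it is why the figures must be reported with their scenarios. But 0.35 is the plan's own target for every cohort, and at that target even winning every tie leaves only 68.8%.

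The ≥4/9 clause is the best remaining point. If a cohort starts early and the other two later score higher, the plan does not say what happens. With all at 0.35, the three cohorts all reach ≥4/9 in 6.0% of trials. Other readings of the clause, with ties otherwise random, move the all-0.35 figure to between 57.5% and 63.3%. That affects the exact number to print, not the conclusion.

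Finally, no section calls a cohort closed by ranking negative, and response rates will be reported within each cohort. The misreading is a risk the plan leaves open, not one it commits.

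**Conclusion.** The concern holds. The 80% in 8.1.2 is the power of one cohort considered alone (81.1% exactly), not of the rule in 8.1.1 and 1.6. Under that rule a cohort at 0.35 has power between 61.4% and 79.4% in the four scenarios examined. The loss is small when it is the only active cohort and largest when all three are active. The figures rest on random tie-breaking, on the assumed rates in the other cohorts, and on reading the ≥4/9 clause as timing only. The whole loss comes from cohorts not advanced; type I error is not inflated. It should be fixed, because the plan claims a property that its full decision rule does not have, and because the missing tie rule would matter in about one trial in four if all cohorts are at 0.35.

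**What to change.** - **8.1.2, power.** State both figures with their assumptions. For example: taken alone, each cohort has 81% power at a response rate of 0.35; because at most two cohorts enter stage 2, and with ties broken at random, power for such a cohort is 61% if both others are at 0.35, 76% if one is at 0.35 and one at 0.15, 73% if both are at 0.25, and 79% if both are at 0.15.
- **8.1.2, independence.** Replace the claim with a sentence saying that each cohort has its own futility and success boundaries, while entry to stage 2 also depends on ranking across cohorts.
- **8.1.1 and 1.6.** Add a tie-breaking rule for the last stage 2 place, and say whether a cohort that starts early under the ≥4/9 clause keeps its place. Recompute the figures if ties are not broken by random draw or if that clause affects more than timing.
- **Reporting.** State that a cohort with 2 or more responses among 9 that is closed by ranking is reported as not advanced, not as a negative test with 80% power.

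The cost is a few sentences in three sections. No patients are added, and no boundary nor the maximum of 77 changes. The stated power becomes less favourable.

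### The formal toxicity looks (6, 12, 18, 24, 30) skip the stage 1 decision at 9 patients and never cover patients 31 to 34, and neither go rule carries a toxicity condition

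*Combined protocol and SAP*

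**What the plan says.** Section 8.1.3 sets one rule for each cohort separately ("Cohorts will be monitored independently"): stop when the posterior probability that the DLT rate exceeds 30% is above 0.90, "using a prior of beta (0.6, 1.4) for toxicity". Coverage is described as "DLT will be monitored continuously in cohorts of 6 subjects for all 34 subjects to ensure safety". The boundaries listed are 4/6, "6/12, 9/18, 11/24, and 13/30". Toxicity reports to the IND Office are due as follows: "After the first 6 evaluable patients per cohort, complete 4 weeks of study treatment, and every 6 evaluable patients thereafter". After 30 the next would fall at 36, beyond the cohort maximum of 34.

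Efficacy runs on a different clock. Reports are due at 9 patients and every 5 thereafter (14, 19, 24, 29, 34), which coincides with a toxicity look only at 24. Under Section 8.1.1, stage 2 requires at least 2 responses in 9 and a place among the two best cohorts (a cohort with 4 or more of 9 may go ahead early). At the end, "If there are 9 or more responses out of 34, the combination will be deemed worthy of further study". Neither rule mentions DLTs. Section 8.1.2 halts accrual while the stage 1 decision is made.

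**The concern.** The plan makes two go decisions per cohort, at 9 and at 34, and has no formal toxicity look at either. A cohort could meet the plan's own stopping criterion when stage 2 opens, or when the combination is called worthy of further study, without any rule bringing this to notice. In a cohort that ends at stage 1, patients 7 to 9 never enter a formal look. In a cohort that runs to completion, patients 31 to 34 never do. The commitment to all 34 subjects is therefore not met by the boundaries as written. The combination is new in this population (Section 1.3.1), and the benefit-risk section accepts that additive or synergistic toxicity is possible.

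**Working it through.** **Inputs (Section 8.1.3).** Prior beta(0.6, 1.4); threshold rate 0.30; cut-off 0.90; looks at 6, 12, 18, 24 and 30; maximum 34.

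**Formula.** With x DLTs in n patients, the posterior tail is 1 − F(0.30), where F is the distribution function of beta(0.6 + x, 1.4 + n − x). The boundary is the smallest x with a tail above 0.90.

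**Step 1: reproduce the stated boundaries.** The tail is 0.945 at 4/6, 0.905 at 6/12, 0.951 at 9/18, 0.938 at 11/24 and 0.929 at 13/30. One DLT fewer gives 0.800, 0.772, 0.883, 0.871 and 0.863. All five boundaries are confirmed.

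**Step 2: reproduce Table 5.** Exact binomial recursion over 34 patients, with looks only at those five points:

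| True DLT rate | Table 5 P(stop) | Recomputed |
|---|---|---|
| 10% | 0.002 | 0.002 |
| 20% | 0.035 | 0.033 |
| 30% | 0.196 | 0.196 |
| 40% | 0.549 | 0.555 |
| 50% | 0.877 | 0.875 |

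A look at 34 would give 0.618 at 40%. Looks after every patient from the sixth would give 0.275 at 30% and 0.672 at 40%. Table 5 fits neither, so it was computed for looks at 6 to 30 only.

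**Step 3: the same criterion at the decision points.** At 9: 4/9 gives 0.782 and 5/9 gives 0.922, so the boundary is 5. At 34: 13/34 gives 0.832 and 14/34 gives 0.9055, so the boundary is 14.

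**Step 4: the gap at 9.** To pass at 6 and reach at least 5/9, a cohort needs 3/6 then at least 2/3, or 2/6 then 3/3. At a 40% rate:

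- 3/6 then at least 2/3: 0.2765 × 0.352 = 0.0973
- 2/6 then 3/3: 0.3110 × 0.064 = 0.0199
- Sum: 0.117

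The same sum is 0.049 at 30% and 0.186 at 50%.

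The look at 12 recovers most of these. A cohort at 6/9 has already reached the boundary for 12. A cohort at 5/9 needs one more DLT in three patients, probability 1 − 0.6³ = 0.784 at a 40% rate. With 0.0995 of the probability at 5/9 and 0.0177 at 6/9, the recovered share is (0.0995 × 0.784 + 0.0177) / 0.1172 = 0.82. At 30% and 50% it is 0.69 and 0.90. The chance of crossing at 9 and also passing 12 is 1.5%, 2.2% and 1.8%.

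**Step 5: the gap at 34.** A cohort at 12/30 continues (0.863), and two more DLTs in the last four patients give 14/34. The probability of never stopping yet ending with at least 14/34 is 0.022, 0.063 and 0.044 at 30%, 40% and 50%.

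**Step 6: effect of adding looks, P(stop or flag).**

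| True DLT rate | Stated looks | Add 9 | Add 34 | Add both |
|---|---|---|---|---|
| 10% | 0.002 | 0.002 | 0.002 | 0.002 |
| 20% | 0.033 | 0.038 | 0.034 | 0.039 |
| 30% | 0.196 | 0.208 | 0.218 | 0.229 |
| 40% | 0.555 | 0.565 | 0.618 | 0.627 |
| 50% | 0.875 | 0.879 | 0.919 | 0.921 |

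**Step 7: joint with response.** The documents give no correlation between DLT and response, so independence is assumed here. The chance of at least 2/9 responses is 0.879 at an ORR of 0.35 and 0.401 at 0.15. The chance of passing the whole response rule is 0.811 and 0.047. At a 40% DLT rate:

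- Crossing at 9 and meeting the stage 1 response rule, before ranking: 0.117 × 0.879 = 0.10, or 0.117 × 0.401 = 0.05
- Ending at 14/34 or more and being deemed worthy: 0.063 × 0.811 = 0.05, or 0.063 × 0.047 = 0.003

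**The case against.** Looks every six patients are a disclosed choice: boundaries, report schedule and Table 5 agree with one another. The look at 9 adds little, between 0.4 and 1.2 points of P(stop) at rates of 30% to 50%, because 12 follows three patients later. The look at 34 protects nobody from enrolment. At a 20% DLT rate, crossing at 9 has probability 1.1% and the gap at 34 about 0.1%. All of this stands, and it limits the size of the point.

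It could also be said that monitoring described as continuous lets the criterion apply at any number of patients. The same sentence ties it to groups of six, and Table 5 does not fit that reading. If it is intended, the boundary list and Table 5 are incomplete, so the section needs editing either way.

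A reader might go further and infer that toxicity is unmonitored at 9 and after 30. The documents do not support that. Events of special interest are reported within 24 hours (Section 7.5), SAEs go to the IND Office (7.2), selected Grade 3 or greater events are reported within 72 hours (7.6.6), and case histories are reviewed monthly (9.5). All treated patients enter the safety analysis (8.2.2). Section 1.3.2 also lets the secondary endpoints inform whether further studies are warranted. What is missing is the formal boundary.

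**Conclusion.** The point holds, with modest size. The plan promises DLT monitoring for all 34 subjects but applies its rule to at most 30, with none at the stage 1 decision. At 9 the consequence for a continuing cohort is mainly a three-patient delay. At 34 it bears on the conclusion: a cohort can be called worthy of further study on responses while meeting the plan's own toxicity criterion.

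It would be tempting to read 4.9%, 11.7% and 18.6%, or 2.2%, 6.3% and 4.4%, as the chances that a too-toxic cohort is advanced or endorsed. They are not: they describe DLT counts alone, and the joint chances with the response rules (and, at stage 1, the ranking) are smaller.

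The figures assume independent patients with a constant DLT rate, and every one of the 34 evaluable for DLT. The last assumption is unsettled, because Section 6.7.2 ties the DLT evaluation period to the first six patients. The figures count boundary crossings only. Section 8.1.3 halts the trial on a crossing, whereas the text under Figure 1 leads from the first crossing to a revised dosing schedule. The calculation does not depend on which applies.

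**What to change.** 1. In Section 8.1.3, add two boundaries from the existing prior and cut-off: at least 5/9, checked before stage 2 opens, and at least 14/34, reported as a flag alongside any conclusion that the combination is worthy of further study.
2. Add the 9- and 34-patient points to the toxicity report schedule.
3. Recompute Table 5. P(stop or flag) becomes about 0.002, 0.039, 0.229, 0.627 and 0.921 at true rates of 10% to 50%.
4. Reconcile the DLT evaluation period in Section 6.7.2 with the monitoring of all 34 subjects in 8.1.3, so that the added boundaries have a defined numerator.

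No new threshold, patients or data are needed. Accrual is already halted at 9, and that decision follows 8 weeks of treatment. With durvalumab first scheduled at Week 4, a four-week window closes after about 3 + 4 = 7 weeks if there is no delay in dosing. The price is a crossing probability of 22.9% instead of 19.6% when the true DLT rate is exactly 30%, and 3.9% instead of 3.3% at 20%.
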